Note: the progression from 0% to 95% looks like a straight line on a semi-log plot with no evidence of a plateau.

TOTAL PATIENTS THAT RESPONDED TO FIRST-LINE CHEMOTHERAPY (CR/PR/SD) (n = 36)

Progressed: 34 of 36 (94.4%)
Not progressed: 2 of 36 (5.5%) (1 CR and 1 PR)

Time to progression among “chemo responders”:
50% (median) progressed 145 days
 50% (median) of CR patients = 303 days
 50% (median) of PR patients = 145 days
 50% (median) of SD patients = 132 days
80% progressed = 288 days
90% progressed = 316 days
94.4% progressed = 466 days

[figure not shown]

Figure 1: First-line chemotherapy and progression-free survival (PFS) in MCC patients with metastatic disease.

These data are derived from 58 patients in the Seattle cohort who developed distant metastatic disease, received first-line chemotherapy, and had evaluable metastatic lesion(s) that were not also treated with radiation or surgery (allowing the effects of chemo-mono-therapy to be evaluated). The vertical axis represents the number of DAYS between the start of first-line chemotherapy and progression (or death). Etoposide was combined with a “platin” in the 40 cases shown as blue bars. Among these 40 cases, the “platin” was carboplatin in 29 cases and cisplatin in 11. Patients 57 and 58 (asterisks) are the only ones who did not progress on chemotherapy or die, as of most recent data. Median PFS was 98.5 days from start of chemotherapy to progression or death. These 58 patients are a subset of the 179 patients we recently reported in which median OS was 289 days (9.5 months) from the date when distant disease was identified (Figure 3).

[figure not shown]

Figure 2: Progression-free survival (PFS) in MCC patients with metastatic disease, treated with first-line chemotherapy and responded with CR, PR, or SD.

These data represent the 36 “chemo responders” among the full cohort of 58 chemotherapy-treated patients in the Seattle cohort shown in Figure 1. Specifically, these 36 patients developed distant metastatic disease, received first-line chemotherapy, and achieved a complete or partial response. The vertical axis represents the number of DAYS between the start of first-line chemotherapy and progression (or death). Median PFS was 145 days from start of chemotherapy to progression or death. These 36 patients are a subset of the 179 patients with distant disease shown in Figure 3.

[figure not shown]

Figure 3: Disease-specific survival in patients who developed metastatic MCC.

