11.1.4.3 Evaluation of Best Overall Response (RECIST)

The best overall response is the best response recorded from the start of the treatment until disease progression/recurrence (taking as reference for PD the smallest measurements recorded since the treatment started). The patient’s best response assignment will depend on the achievement of both measurement and confirmation criteria.

For Patients with Measurable Disease (i.e., Target Disease)

Target Lesions	Non-Target Lesions	New Lesions	Overall Response	Best Overall Response when Confirmation is Required*
CR	CR	No	CR	≥4 wks Confirmation**
CR	Non-CR/Non-PD	No	PR	≥4 wks Confirmation**
CR	Not evaluated	No	PR	
PR	Non-CR/Non-PD /not evaluated	No	PR	
SD	Non-CR/Non-PD /not evaluated	No	SD	Documented at least once ≥4 wks from baseline**
PD	Any	Yes or No	PD	no prior SD, PR, or CR
Any	PD***	Yes or No	PD	
Any	Any	Yes	PD	

* See RECIST 1.1 manuscript for further details on what is evidence of a new lesion. ** Only for nonrandomized trials with response as primary endpoint. *** In exceptional circumstances, unequivocal progression in non-target lesions may be accepted as disease progression.
 
Note: Patients with a global deterioration of health status requiring discontinuation of treatment without objective evidence of disease progression at that time should be reported as “symptomatic deterioration.” Every effort should be made to document the objective progression even after discontinuation of treatment.
				

For Patients with Nonmeasurable Disease (i.e., Non-Target Disease)

Non-Target Lesions	New Lesions	Overall Response
CR	No	CR
Non-CR/non-PD	No	Non-CR/non-PD*
Not all evaluated	No	not evaluated
Unequivocal PD	Yes or No	PD
Any	Yes	PD

* “Non-CR/non-PD” is preferred over ‘stable disease’ for non-target disease since SD is increasingly used as an endpoint for assessment of efficacy in some trials so to assign this category when no lesions can be measured is not advised
		

11.1.5 *Progression-Free Survival*

PFS is defined as the duration of time from start of treatment to time of progression or death, whichever occurs first.

11.1.6 *Duration of Response*

The duration of overall response is measured from the time measurement criteria are met for CR or PR (whichever is first recorded) until the first date that recurrent or progressive disease is objectively documented (taking as reference for PD the smallest measurements recorded since the treatment started).

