13.3 Analysis Endpoints

13.3.1 *Efficacy Endpoints*

The primary and secondary efficacy endpoints are described below.

Objective response rate (ORR) is defined as the proportion of patients who have achieved CR or PR according to RECIST 1.1.

Progression-Free Survival (PFS) is defined as the time from randomization to PD or death, whichever occurs earlier, based upon investigator assessment using RECIST 1.1. Patients without documented PD/death will be censored at the last disease assessment date.

Duration of response (DOR) is defined as the time interval between the date of first response (CR/PR) and the date of progression.

Overall survival (OS) is defined as the time from randomization to death due to any cause. Patients without documented death at the time of analysis will be censored at the date last known to be alive.

13.3.2 *Safety Endpoints*

The primary safety endpoints are AEs graded using CTCAE (Version 5.0) criteria. Safety will be assessed by quantifying the toxicities and grades experienced by subjects who have received MK-3475 including AEs and SAEs. Safety will be monitored by cumulative data reviews throughout the trial.

Other safety endpoints include laboratory safety assessments, ECOG performance status, vital signs, and physical examinations.

Note: Patients discontinuing MK-3475 due to toxicity will still be considered evaluable for response.

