Note: Patients with confirmed progression will be declared as having progressive disease for statistical purposes even if they remain on study and respond continued MK-3575. Responses to continued MK-3575 will be chronicled and reported.

13.5.1.2 **PFS, DOR, and OS**

Survival curves for PFS, DOR, and OS will be estimated using the Kaplan-Meier

method.

For PFS, subjects without documented PD/death will be censored at the last disease assessment date. Any subject who is lost to follow-up will be included in the analysis and their PFS time will be censored on the last date that the subject was known to be progression-free, defined as the date of the last tumor assessment not indicating progression. As a sensitivity analysis, the primary analysis of PFS will be performed reconsidering subjects without documented PD or death who discontinued treatment or received new anticancer therapy to have been progressed at the date of treatment discontinuation or initiation of new anticancer therapy, whichever occurs later.

For OS, subjects without documented death at the time of analysis will be censored at the date last known to be alive.

For DOR, subjects who have not yet progressed by the last disease assessment will be censored at the last disease assessment—this is intended to describe censoring rules for the analysis where only responders are used.

Table 13.1 Analysis Strategy for Key Efficacy Variables

Endpoint/Variable (Description, Time point)	Statistical Method	Analysis Population	Missing Data Approach
Primary Hypothesis			
ORR	Simon Two Stage design analysis	Eligible subjects who receive at least 1 dose of treatment	See 13.5.1.
Secondary Objectives			
PFS	Estimation: Kaplan-Meier method for PFS curve estimation	Eligible subjects who receive at least 1 dose of treatment	Model based (censored at last assessment)
DOR	Summary statistics using Kaplan-Meier method	All responders	Nonresponders are excluded in analysis
OS	Summary statistics using Kaplan-Meier method	Eligible subjects who receive at least 1 dose of treatment	Model based (censored at last date)
Exploratory Objectives			

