13.13 Reporting and Exclusions

13.13.1 Evaluation of Toxicity

All patients will be evaluable for toxicity from the time of their first treatment with MK-

3475.

13.13.2 *Evaluation of Response*

All patients included in the study must be assessed for response to treatment, even if there are major protocol treatment deviations or if they are ineligible. Each patient will be assigned one of the following categories: (1) CR, (2) PR, (3) SD, (4) PD, (5) early death from malignant disease, (6) early death from toxicity, (7) early death because of other cause, or (9) unknown (not assessable, insufficient data).

Note: By arbitrary convention, category 9 usually designates the “unknown” status of any type of data in a clinical database.

All of the patients who met the eligibility criteria (with the exception of those who received no study medication) should be included in the main analysis of the response rate. Patients in response categories 4–9 should be considered to have a treatment failure (disease progression). Thus, an incorrect treatment schedule or drug administration does not result in exclusion from the analysis of the response rate. Precise definitions for categories 4–9 will be protocol specific.

All conclusions should be based on all eligible patients. Subanalyses may then be performed on the basis of a subset of patients, excluding those for whom major protocol deviations have been identified (e.g., early death due to other reasons, early discontinuation of treatment, major protocol violations, etc.). However, these subanalyses may not serve as the basis for drawing conclusions concerning treatment efficacy, and the reasons for excluding patients from the analysis should be clearly reported. The 95% confidence intervals should also be provided.

REFERENCES

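### Duration of response ends at progression only, so a responder who dies without documented progression is censored in DOR although that death is a PFS event; a progression-or-death DOR should be reported beside it.

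*Combined protocol and SAP*

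**What the plan says.** **DOR.** Section 13.3.1: "Duration of response (DOR) is defined as the time interval between the date of first response (CR/PR) and the date of progression". Section 11.1.6 runs DOR from the first recorded CR or PR "until the first date that recurrent or progressive disease is objectively documented". Under Section 13.5.1.2, "subjects who have not yet progressed by the last disease assessment will be censored at the last disease assessment"; that sentence makes no exception for death. Table 13.1 summarises DOR by Kaplan-Meier among responders only.

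**PFS.** Section 11.1.5: "PFS is defined as the duration of time from start of treatment to time of progression or death, whichever occurs first". Section 13.3.1 also ends PFS at progression or death and adds: "Patients without documented PD/death will be censored at the last disease assessment date".

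**Status of DOR.** It is a secondary endpoint (Sections 1.2 and 13.2.2) with no test, target or decision rule. The planned comparison with historical chemotherapy is PFS at 16 months.

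**Where changes can be made.** The opening of Section 13 says there will be no separate SAP, so Section 13 and the definitions in Section 11 are the whole plan for this endpoint.

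**The concern.** Kaplan-Meier treats a censored responder as someone whose response could have continued beyond the censoring date. That does not describe a patient who has died. The plan avoids this in PFS by counting the death, but not in DOR, and it neither labels nor explains the difference.

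At stake is how a reader understands the durability of response, which is part of the trial's hypotheses (Sections 1.1 and 1.2). DOR is the only planned measure that starts at response and is restricted to responders. PFS and OS record these deaths but do not show how long responses lasted with death counted. Any discrepancy goes one way, towards a longer DOR, and a confidence interval around the progression-only curve would not reveal it.

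Such deaths are possible. Section 2.4 describes an older population, and Section 5.5 allows scans six months apart in post-treatment years 2 and 3.

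**Working it through.** The documents give no DOR estimate, target or sample size, so there is no figure of the plan's own to reproduce. The check has two parts.

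**1. The event rules side by side**

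| | DOR (11.1.6, 13.3.1, 13.5.1.2) | PFS (11.1.5, 13.3.1, 13.5.1.2) |
|---|---|---|
| Ending event | Progression | Progression or death |
| Who is censored | Every responder not yet progressed | Only patients with neither progression nor death |
| Responder dies without documented progression | Censored at last assessment | Event at death |

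Three other provisions could have closed the gap, and none does:
- The sensitivity analysis in 13.5.1.2 that adds events is written for PFS and for patients who have not died: "As a sensitivity analysis, the primary analysis of PFS will be performed reconsidering subjects without documented PD or death who discontinued treatment".
- The missed-visit analysis under Table 13.1 adds censoring, not death events.
- Section 13.13.2 counts the early-death categories as treatment failures, but for the response rate. It does not reach a patient already classed as CR or PR who dies later.

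**2. The effect of one such death**

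Let n responders be at risk at the patient's last assessment, including the patient. Let k others progress between that assessment and the death, with no other censoring in between.

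- Progression-only: the patient leaves the risk set, so the curve is multiplied by (n − 1 − k)/(n − 1).
- Progression-or-death: the curve is multiplied by [(n − k)/n] × [(n − k − 1)/(n − k)] = (n − 1 − k)/n.
- Ratio of the second to the first: (n − 1)/n, a relative drop of 1/n. It stays constant afterwards, because the two risk sets are then the same.

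Example with n = 28 and k = 4: 23/27 = 0.852 against 23/28 = 0.821, a ratio of 27/28 = 0.964.

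If others are censored in the interval, the drop is at least 1/n at the last assessment and at most 1/n at the death. The direction never reverses from the date of death onward.

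**Inputs**
- Enrolment: 50 (Study Summary; Section 13.7).
- Responders, assumed: Section 2.1.7 gives 8 CR and 24 PR among 58 chemotherapy patients, (8 + 24)/58 = 55.2%. Section 2.4.1 says response in this trial was running better than historical chemotherapy. 0.552 × 50 = 27.6, taken as 28.
- Curve height, assumed for illustration: 75%.

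**Results per death**
- All 28 at risk: 1/28 = 3.6% relative; 0.75/28 = 2.7 points.
- Half (14) at risk: 1/14 = 7.1% relative; 0.75/14 = 5.4 points.
- Approximate 95% half-width at 75%, ignoring earlier censoring: 1.96 × √(0.75 × 0.25/28) = 16.0 points.

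**The case against.** The strongest reply is that nothing is broken. The DOR passages agree with each other, the end event and the censoring rule are written down, and a progression-only DOR is a coherent measure. DOR decides nothing, OS captures every death, and PFS captures a responder's death without progression. The plan also makes undocumented disease deaths less likely: Section 11.1.4.3 asks for effort to document progression after treatment stops, Section 5.5 allows imaging when clinically indicated, and Section 7.3.3 asks for evidence when a death is attributed to disease. Finally, the opening of Section 13 lets changes to non-confirmatory analyses be listed in the clinical study report.

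All of this stands, and it limits the weight of the point. It does not remove the gap: deaths from other causes remain possible, and no planned analysis counts them in DOR.

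A reader might also infer three stronger things, which the documents do not support:

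- **That DOR is biased against the chemotherapy benchmark.** The Figure 2 legend in Section 2.1.7 does say "Median PFS was 145 days from start of chemotherapy to progression or death", but the same section lists the 145 days, with separate CR, PR and SD medians (303, 145 and 132 days), as time to progression. The figure carries both labels, starts at chemotherapy rather than at response, and includes SD. No DOR comparison with chemotherapy is planned.
- **That one death could move the curve by as much as 12.5 points.** That needs 12 responders (25% of 50, the design alternative) with half at risk: 0.75/6. Section 2.4.1 reports response above both expectation and historical chemotherapy, so 12 is not a fair basis.
- **That the PFS rules should simply be copied to DOR.** The PFS sensitivity rule counts patients who stop treatment as progressed. Sections 5, 5.1.1 and 5.9 let complete responders stop and end treatment at 24 months, so ongoing responses would become failures.

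**Conclusion.** The gap is real but modest. A responder's death without documented progression is censored in DOR and counted in PFS, and nothing else in the plan repairs this.

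The total effect cannot be derived, because the documents give no number or rate of such deaths; it is zero if there are none. Per death it is about 3.6% to 7.1% relative, or 2.7 to 5.4 points at a curve height of 75%. Those figures rest on two assumptions, 28 responders and that height. If the early response rate held and there are more responders, the effect per death is smaller. One such shift is well inside the sampling uncertainty of about 16 points, but unlike sampling error it has only one direction.

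This is not a contradiction within the DOR text, nor a threat to the trial's main conclusions: the ORR test and the 16-month PFS comparison do not depend on DOR. The change is worth making because it is cheap and leaves the reader in no doubt about what DOR measures.

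**What to change.** In Sections 11.1.6, 13.3.1 and 13.5.1.2:

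1. Keep the existing definition and label it progression-only DOR, with death censored.
2. Beside it, add DOR as time from first CR or PR to progression or death from any cause, whichever is first. Censor only responders alive without progression, at their last disease assessment.
3. Report the number of responders who died without documented progression.
4. Disclose that the progression-or-death version was added after response data had been reviewed (Section 2.4.1), in keeping with the opening of Section 13 on changes to analyses.

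Do not carry the PFS sensitivity rule on treatment discontinuation or new therapy over to DOR.

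**Cost.** Wording in three sections and one extra analysis. No new data are needed, since Section 5.5 already has time to death recorded for every patient. The downsides are a post hoc disclosure and a second DOR that may be slightly shorter.

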13.4 Analysis Populations

13.4.1 *Efficacy Analysis Population*

The population of eligible subjects who receive at least 1 dose of treatment will serve as the primary population for the analysis of efficacy data in this study.

13.4.2 *Safety Analysis Population*

The All Subjects as Treated (ASaT) population will be used for the analysis of safety data in this study. The ASaT population consists of all patients who received at least 1 dose of study treatment. . Patients who do not receive the study treatment will be excluded from analysis.

At least one laboratory or vital sign measurement obtained subsequent to at least 1 dose of study treatment is required for inclusion in the analysis of each specific parameter. To assess change from baseline, a baseline measurement is also required.

13.5 Statistical Methods

The protocol has a standard Simon two stage design. The null hypothesis that the true response rate is 5% will be tested against a one-sided alternative. In the first stage, 9 patients will be accrued. If there are no responses in these 9 patients, the study will be stopped. Otherwise, 15 additional patients will be accrued for a total of 24. The null hypothesis will be rejected if 3 or more responses are observed in 24 patients. This design yields a type I error rate of 0.10 and power of 0.90 when the true response rate is 25%. PFS at 16 months will be estimated by Kaplan-Meier method.

The current protocol will increase the total number of patients from 26 to 50. The initial protocol enrolled nine subjects in Stage 1, and planned to enroll an additional 15 subjects in Stage 2 for a total enrollment of 24. Treatment was discontinued in 2 patients due to drug-related adverse events after receiving 1 dose of MK-3475, and enrollment of an additional 2 patients was allowed per protocol, bringing the total enrollment to 26 patients. The current protocol amendment will increase the total number to 50 to provide an expanded safety and efficacy profile.

Unless otherwise stated, all statistical tests will be conducted at the $\alpha=0.05$ (1-sided) level.

13.5.1 *Statistical Methods for Efficacy Analyses*

13.5.1.1 **ORR**

ORR will be estimated as the number of responders as a percent of the number of eligible participants who received at least 1 dose of treatment. If a substantial amount of primary endpoint data are missing (at least 1 value missing from more than 20% of participants), using nonparametric estimation to estimate the ORR requires the missing completely at random assumption may give misleading results. In this situation, analyses of the primary endpoint at the primary time point will be performed using parametric generalized linear models fit by maximum likelihood. These methods provide unbiased estimation and inferences under the parametric modeling assumptions and the assumption that the missing data are missing at random (MAR). MAR assumes that the probability of an observation being missing may depend upon the observed responses and upon observed covariates, but not upon any unobserved factors. A generalized linear model for the ORR will use a binomial error distribution. The model will include as covariates all available baseline predictors of the missing outcomes.

Note: Patients with confirmed progression will be declared as having progressive disease for statistical purposes even if they remain on study and respond continued MK-3575. Responses to continued MK-3575 will be chronicled and reported.

13.5.1.2 **PFS, DOR, and OS**

Survival curves for PFS, DOR, and OS will be estimated using the Kaplan-Meier

method.

For PFS, subjects without documented PD/death will be censored at the last disease assessment date. Any subject who is lost to follow-up will be included in the analysis and their PFS time will be censored on the last date that the subject was known to be progression-free, defined as the date of the last tumor assessment not indicating progression. As a sensitivity analysis, the primary analysis of PFS will be performed reconsidering subjects without documented PD or death who discontinued treatment or received new anticancer therapy to have been progressed at the date of treatment discontinuation or initiation of new anticancer therapy, whichever occurs later.

For OS, subjects without documented death at the time of analysis will be censored at the date last known to be alive.

For DOR, subjects who have not yet progressed by the last disease assessment will be censored at the last disease assessment—this is intended to describe censoring rules for the analysis where only responders are used.

Table 13.1 Analysis Strategy for Key Efficacy Variables

Endpoint/Variable (Description, Time point)	Statistical Method	Analysis Population	Missing Data Approach
Primary Hypothesis			
ORR	Simon Two Stage design analysis	Eligible subjects who receive at least 1 dose of treatment	See 13.5.1.
Secondary Objectives			
PFS	Estimation: Kaplan-Meier method for PFS curve estimation	Eligible subjects who receive at least 1 dose of treatment	Model based (censored at last assessment)
DOR	Summary statistics using Kaplan-Meier method	All responders	Nonresponders are excluded in analysis
OS	Summary statistics using Kaplan-Meier method	Eligible subjects who receive at least 1 dose of treatment	Model based (censored at last date)
Exploratory Objectives			
PFS and OS by the following biomarker categories: 
 • pre-therapy CD8+ • pre-therapy CD3+ T-cell infiltration in tumor • pre-therapy PD-1 and PD-L1 expression in tumor, 
 • * pre-therapy immune response to MCPyV 	Descriptive statistics	Eligible subjects who receive at least 1 dose of treatment	censored at last assessment

ORR by the following biomarker categories:
 
 • pre-therapy CD8+ • pre-therapy CD3+ T-cell infiltration in tumor • pre-therapy PD-1 and PD-L1 expression in tumor, 
* pre-therapy immune response to MCPyV
	
Descriptive statistics
	
Eligible subjects who receive at least 1 dose of treatment
	
Missing value considered nonresponder

--	-------------------------------	---	--

Note: PD after 1 or more missed visits will be counted as PD as of the date of documented disease progression. An additional sensitivity analysis will be performed where subjects with 2 or more missed visits before progression will be censored at the last disease assessment before the ≥ 2 missed disease assessments.

13.5.2 *Statistical Methods for Safety Analyses*

Safety and tolerability will be assessed by clinical review of all relevant parameters including adverse experiences, laboratory tests, vital signs, and ECG measurements.

Adverse experiences will be summarized as counts and frequencies by toxicity grade. Summary statistics (median and range) for time to onset of first drug-related toxicity will be provided.

Laboratory assessments, vital signs, and other safety endpoints will be summarized using descriptive statistics as appropriate.

13.5.3 *Summaries of Baseline Characteristics, Demographics, and Other Analyses*

The number and percentage of subjects enrolled, and the primary reason for discontinuation will be displayed. Demographic variables (such as age) and baseline characteristics will be summarized either by descriptive statistics or categorical tables. No statistical hypothesis tests will be performed on these characteristics.

13.6 **Multiplicity**

The treatment comparison will be tested at one sided 5% alpha level and no multiplicity adjustment will be applied.

13.7 **Sample Size/Accrual Rate and Power Calculations**

To date, the trial has enrolled 26 patients. The initial plan was to “enroll between 9 and 24 subjects to receive MK-3475 in a two-stage Simon design with 90% power to reject the null hypothesis of a 5% true response rate against a 1-sided alternative when the true response rate is 25%. The study will enroll the first 9 patients over a 6-month period, followed by enrollment of 15 more subjects over 10 months”.

“In the first stage, 9 patients will be accrued. If there are no responses in these 9 patients, the study will be stopped. Otherwise, 15 additional patients will be accrued for a total of 24. The null hypothesis will be rejected if 3 or more responses are observed in 24 patients. This design yields a type I error rate of 0.10 and power of 0.90 when the true response rate is 25%”.

The current protocol amendment will increase the total number of patients to 50 to provide an expanded safety and efficacy profile. The analysis will utilize the same statistical test.

Accrual Targets				
Ethnic Category	Sex/Gender			
	Females		Males	Total
Hispanic or Latino		+		=
Not Hispanic or Latino	21	+	29	= 50
Ethnic Category: Total of all subjects	21	+	29	= (50)
Racial Category				
American Indian or Alaskan Native		+		=
Asian	1	+	1	= 2
Black or African American		+	1	= 1
Native Hawaiian or other Pacific Islander		+		=
White	20	+	27	= 47
Racial Category: Total of all subjects	21	+	29	= (50)

(A1 = A2)

(B1 = B2)

(C1 = C2)

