For patients who discontinue trial treatment for reasons other than disease progression, imaging during the post-treatment follow-up period is to continue as described in Section 5.1.1 until confirmed disease progression, start of a new antineoplastic therapy, death or end of study, whichever occurs first.

Local reading (investigator assessment with site radiology reading by RECIST 1.1 criteria) will be used to determine patient eligibility and for patient management. Radiologic images will be collected and stored for a possible retrospective analysis of patient eligibility and treatment response to be performed by a central vendor, including RECIST 1.1.

Evaluable Non-target Disease Response. Patients who have lesions present at baseline that are evaluable but do not meet the definitions of measurable disease, have received at least 1 cycle of therapy, and have had their disease re-evaluated will be considered

evaluative for non–target disease. The response assessment is based on the presence, absence, or unequivocal progression of the lesions.

Patients who do not receive a post-baseline scan due to discontinuing treatment as a result of toxicity should be considered evaluative for response.

11.1.2 *Disease Parameters*

Measurable disease. Measurable lesions are defined as those that can be accurately measured in at least one dimension (longest diameter to be recorded) as ≥ 20 mm by chest x-ray or as ≥ 10 mm with CT scan, magnetic resonance imaging (MRI), or calipers by clinical exam. All tumor measurements must be recorded in millimeters (or decimal fractions of centimeters).

Note: Tumor lesions that are situated in a previously irradiated area or in an area subjected to other locoregional therapy are usually not considered measurable unless there has been demonstrated progression in the lesion.

Malignant lymph nodes. To be considered pathologically enlarged and measurable, a lymph node must be ≥ 15 mm in the short axis when assessed by CT scan (CT scan slice thickness recommended to be no greater than 5 mm). At baseline and in follow-up, only the short axis will be measured and followed.

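### Section 13.5.1.1 switches the primary ORR to a missing-at-random model above 20% missingness, whereas 13.13.2 counts unassessable patients as failures with no threshold

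*Combined protocol and SAP*

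**What the plan says.** Section 13.5.1.1 defines the ORR as responders divided by all eligible participants who received at least one dose. It then sets a trigger for substantial missing data, "at least 1 value missing from more than 20% of participants". Once that is met, "analyses of the primary endpoint at the primary time point will be performed using parametric generalized linear models fit by maximum likelihood". The model is binomial, assumes MAR, and takes as covariates all available baseline predictors of the missing outcomes.

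Section 13.13.2 says that eligible patients, apart from those who received no study drug, "should be included in the main analysis of the response rate". Patients in categories 4 to 9 "should be considered to have a treatment failure (disease progression"). Category 9 is "unknown (not assessable, insufficient data"). No level of missingness is attached to this rule, and no model is mentioned.

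In Table 13.1 the method for the primary ORR is "Simon Two Stage design analysis", and the missing-data column refers to 13.5.1. In the same table, the exploratory ORR by biomarker treats a missing value as nonresponse.

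Two further statements concern toxicity. The note in 13.3.2 reads "Patients discontinuing MK-3475 due to toxicity will still be considered evaluable for response". Section 11.1.1 extends evaluability to "Patients who do not receive a post-baseline scan due to discontinuing treatment as a result of toxicity".

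**The concern.** Both rules apply to the primary ORR in the same population, so this is not a main analysis alongside a sensitivity analysis. Below the trigger they agree, because an all-treated denominator already counts an unassessable patient as a nonresponder. Above it they part: 13.13.2 gives a category 9 patient a response probability of zero, while the fitted model gives that patient a predicted probability above zero.

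The reason 13.5.1.1 gives for switching does not fit its own default. Responders over all treated patients needs no missing-completely-at-random assumption. The trigger is also written for a repeated measurement at a fixed visit. ORR here is a best overall response, so a patient can miss one scan and still have a known outcome, and the primary time point is not defined. The section does not say whether a toxicity patient with no scan counts as missing.

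What is at stake is the reported ORR and its interval. The trial is open-label (13.1) and Section 13 says no separate SAP will be issued, so an analyst could choose between two protocol-supported figures after seeing the data.

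**Working it through.** **Plan's own figure.** The plan gives no missing-data figure. As a check on the binomial calculations, I reproduced the Simon design in 13.5: stop if 0 of 9 respond, reject the null if 3 or more of 24 respond. Summing over stage 1 counts x ≥ 1 of P(X₁ = x) × P(X₂ ≥ 3 − x), with 9 and 15 patients, gives power 0.903 at 25% (stated 0.90) and type I error 0.093 at 5% (stated 0.10, which works as an upper limit). These do not bear on the conflict.

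**Inputs from the documents.** N = 50 (13.7), null rate 5% (13.5), trigger above 20% (13.5.1.1). Since 20% of 50 is 10, the trigger is first met at 11 participants.

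**Inputs assumed.** Responders r and patients with unknown best response m. In every row the trigger is taken as met; when m is below 11, the other participants counted by the trigger have missed a scan but have a known best response.

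**Formulas.** Failure rule: r/50. Binomial model with no covariates: its maximum-likelihood estimate is r/(50 − m). Intervals are exact (Clopper-Pearson).

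| r | m | Failure rule | Model, no covariates |
|---|---|---|---|
| 20 | 0 | 20/50 = 40.0% (95% CI 26.4–54.8) | 20/50 = 40.0% |
| 20 | 3 | 40.0% | 20/47 = 42.6% |
| 20 | 5 | 40.0% | 20/45 = 44.4% (29.6–60.0) |
| 20 | 11 | 40.0% | 20/39 = 51.3% (34.8–67.6) |
| 20 | 15 | 40.0% | 20/35 = 57.1% (39.4–73.7) |
| 12 | 11 | 12/50 = 24.0% | 12/39 = 30.8% |
| 25 | 11 | 25/50 = 50.0% | 25/39 = 64.1% |

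**With a baseline covariate.** The plan requires covariates, so the table is a simplification. Assume 30 good-prognosis patients with 17 responders, 20 poor-prognosis patients with 3 responders, and all unknowns in the poor group. Fit the logistic model to patients with known response and average its predictions over all 50:

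- 5 unknown: (17 + 20 × 3/15)/50 = 21/50 = 42.0%, against 44.4% without the covariate.
- 11 unknown: (17 + 20 × 3/9)/50 = 23.67/50 = 47.3%, against 51.3% without it.

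**Test against 5%.** The exact one-sided p-value is below 0.00001 for every fraction in the table. A conclusion changes only at a low rate: with 5 responders and 11 unknown, 5/50 gives p = 0.104 and 5/39 gives p = 0.044.

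**The case against.** The strongest reply is that precedence is not wholly unstated. Table 13.1 has a missing-data column, and for the primary ORR it names 13.5.1. Section 13.13.2 is worded generically and leaves precise definitions of categories 4 to 9 to the protocol, so the more specific section could be read as governing. This weakens the conflict but does not remove it. No passage takes category 9 out of the failures, and 13.13.2 applies itself expressly to the main response-rate analysis. Reading it the other way, with 13.13.2 applied first so that nothing is missing, leaves the trigger and model as dead text.

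Second, the affected group is narrow. Early deaths have their own failure categories (5 to 7), and toxicity patients stay evaluable. That leaves category 9, plus the doubt about toxicity patients with no scan. The largest gaps need 11 to 15 of 50 patients with no best response, which nothing in the documents supports. If only single scans are missed, the gap is zero. All of this stands and limits the size of the point.

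Third, 13.5.1.1 does not say how an ORR is extracted from the model. Predicting at the mean covariate value can reverse the direction. With an assumed 19/30 responders in one group, 1/15 known in another group of 20, and 5 unknown, the failure rule gives 40.0%, the averaged model 40.7%, and the prediction at the covariate mean 32.6%. But that last quantity does not estimate the population response proportion. The example shows a further gap in the specification, not a defence of it.

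Fourth, the primary test counts observed responders and is essentially untouched. Section 2.4.1 reports a response rate above expectation, so the 5-responder reversal has little relevance. That is accepted.

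**Conclusion.** The concern holds. Sections 13.5.1.1 and 13.13.2 give incompatible rules for the same primary estimate once more than 20% of participants have a missing value and at least one best response is unknown. That 13.13.2 applies at any level of missingness is inferred from the absence of a threshold, which is the natural reading.

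On the assumed 20 responders among 50, the model exceeds the failure rule by about 3 points with 3 unknown, 2 to 4 points with 5, and 7 to 11 points with 11; the lower ends come from the assumed covariate example. The model figure is biased upward against the true rate only if the unknown patients are mostly nonresponders, which is plausible but not stated. The consequence is for the reported ORR and its interval, not for rejection of the 5% null at the response rates expected here. It should be corrected before the final analysis.

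**What to change.** In 13.5.1.1, remove the 20% trigger and the model as the primary analysis. State that eligible treated patients with no post-baseline assessment or an unknown best response count as nonresponders whatever the amount missing, as 13.13.2 already provides. This also settles the status of toxicity patients with no scan. Point the ORR row of Table 13.1 to that rule, which brings it into line with the exploratory ORR row.

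If the MAR model is kept, label it a sensitivity analysis, trigger it on missing best overall response and not on any missing value, and state that the ORR is the average of the predictions over all eligible treated patients.

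Simply naming which section governs would remove the contradiction. Choosing the failure rule is preferable because it is already stated for the main analysis and does not depend on the model or on MAR. The cost is wording in 13.5.1.1 and one row of Table 13.1, and possibly a slightly less favourable ORR. No new data or patients are needed.
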